12.3.4. Expectedness

Category	Definition
Expected	An adverse event that is consistent with the information about DIALIVE listed in the Investigator Brochure (IB) and CIP
Unexpected	An adverse event that is not consistent with the information about DIALIVE listed in the Investigator Brochure (IB) and CIP

The reference document to be used to assess expectedness against the intervention is the IB. The CIP will be used as the reference document to assess disease related and/or procedural expected events.

12.4. Procedures for recording and reporting Adverse Events and Device Deficiencies

12.4.1. Investigator responsibilities:

The site Investigator shall report any SAE, SADE, USADE and DDs which occur in a subject to the Sponsor/CRO immediately but no later than 3 calendar days after site awareness of the event. The immediate report for all events may be made orally or in writing (using the Sponsor's/CRO SAE form or DD form, as applicable) and shall be followed by a detailed written report on the event.

The PI will respond to any queries raised by the Sponsor/CRO as soon as possible.

The Sponsor/CRO will report any SAE or DD to the REC and/or Competent Authority according to national guidelines.

All deaths of a patient during their participation in the study will be reported as a SAE irrespective of whether the death is related to trial participation or an unrelated event.

Where the event reported consists of, or results in the death of a subject, the investigator shall supply the Sponsor/CRO with any additional information requested by the Sponsor/CRO. Where the death has been reported to the relevant ethics committee, the investigator shall supply any additional information requested by that committee. All serious adverse events will be recorded in the hospital notes, the eCRF and a SAE form.

The investigator shall keep detailed records of all adverse events and device deficiencies relating to the clinical investigation, which are reported to them, by trial participants or users. The investigator shall document all relevant information on Sponsor/CRO provided AE logs, SAE forms and DD forms.

12.4.2. Reporting of all Adverse Events and Device Deficiencies: Investigator and Sponsor responsibilities

Investigator responsibilities shall be as per section 13.4. The sponsor shall keep detailed records of all adverse events and device deficiencies relating to the clinical trial, which are reported to them by the trial investigators. The Sponsor/CRO shall ensure that all relevant information about a reportable event, which occurs during the course of this clinical investigation, is reported as soon as possible to the competent authority and relevant ethics committees per their reporting requirements and according to the timelines in section 13.2. Any additional relevant information should be sent within the same time frame as the initial report. The Sponsor/CRO is responsible for informing the appropriate regulatory authorities, ethics committees and other investigators of any reportable events that have

Clinical Investigation Plan CIP YAQ-002 Version: 7.0 10 October	er 2019
---	---------

occurred with the study device in any clinical investigation according to the guidelines set forth by either the ethics committees of record or regulatory authority in the country where the clinical investigation is taking place.

12.4.3. Safety Update Reports

These will be undertaken in accordance with national requirements.

12.4.4. Progress reports

Progress reports will be submitted to the ethics committees yearly as per national requirements. The Sponsor/CRO will prepare and submit the progress reports.

12.5. Foreseeable adverse events and anticipated adverse device effects

Listed below are known complications associated with liver disease

- Gastrointestinal bleeding
- Spontaneous Bacterial Peritonitis (SBP)
- Hepatic Encephalopathy (HE)
- Hypotension
- Septic shock
- Respiratory failure
- Cardiovascular failure
- Renal insufficiency
- Hepatorenal syndrome
- Death

Any existing condition will be recorded at baseline during screening. Further events relating to an existing condition will not be recorded as an AE unless in the opinion of the PI, the condition has worsened since baseline. All AEs will be recorded from the point of consent and reported to the Sponsor in accordance with section 13.2.

During initial human dialysis sessions, and subsequent DSMB reviews, the following (potential) device related SAEs were observed; these were incorporated in the latest version of the Investigator Brochure:

- Hypotension: this resulted in a series of recommendations to follow during the DIALIVE treatment (see §3.2 of CIP)
- Higher then expected albumin drop during dialysis led to additional in vitro tests supporting the need to administer
 g albumin every hour of dialysis (see §3.4 of CIP and §8.1 of IB)
- Anemia was observed in one patient, requiring blood cell pack administration to restore the hemoglobin level. (see page §3.2 of CIP and §9.1, 11.2 and 12.3i of IB)

Reference is made to section 3.2 of this document, where also the anticipated events related to extracorporeal circulation and to kidney dialysis are summarized

Clinical Investigation Plan CIP YAQ-002 Version: 7.0 10 0	October 2019
---	--------------

12.6. Emergency contact details for reporting serious adverse events, serious adverse device effects and device deficiencies.

All SAEs and USADEs will be reported to the CRO via the eCRF. In the event access to the eCRF is not available, paper SAE forms will be completed by the site and emailed to:

[contact]

or via fax ([contact]).

Please refer to Appendix 6 for Country Specific Safety Reporting.

13. VULNERABLE POPULATION

Many subjects able to consent for themselves will be enrolled in the investigation. To provide additional protection of subjects, each subject will nominate a consultee at the point of consent who, should the patient loose capacity during the study, can act under their presumed wishes of the subject and ensure any study intervention conducted will have the consent of the consultee. If the patient does not have a consultee then they may be offered a professional consultee (independent of the study). In all instanties, the treating physician is required to adhere to Good Clnical Practices, i.e. to offer the best care at all times to the patient, irrespective of his/her study participation and health condition. Only if the national and/or local Ethics Committee does have legislation to allow the inclusion of unconscious patients, then these patients fulfilling all other in/exclusion criteria can be considered for study participation. All applicable regulations will need to be implemented prior study inclusion of this kind of vulnerable patient; if regulations cannot be fully complied with then the patient will not be considered for study inclusion. The possibility to include these vulnerable patients will be assessed and documented upfront prior first study patient enrollment in a given center.

14. SUSPENSION OR PREMATURE TERMINATION OF THE CLINICAL INVESTIGATION

The Sponsor may suspend or prematurely terminate either the clinical investigation in an individual investigation site or the entire clinical investigation for significant and documented reasons.

The PI, ethics committee, or regulatory authority may suspend or prematurely terminate participation in a clinical investigation at the investigation sites for which they are responsible.

If suspicion of an unacceptable risk to subjects arises during the clinical investigation, the Sponsor will suspend the clinical investigation while the risk is assessed. All information will be sent to the Data Safety Monitoring Board (DSMB) for review. The Sponsor shall;

- a) Terminate the clinical investigation if an unacceptable risk is confirmed by the DSMB. All other Investigators will be informed or
- b) If following review the DSMB concludes appropriate corrective actions have been undertaken and are acceptable and decides to lift the temporary suspension, the Sponsor will obtain all the necessary approvals for re-instating the trial and will inform all Principal Investigators.

The reports of the DSMB outcome will be forwarded to the national Competent Authority. The outcome will be implemented as a protocol amendment after the 1st and 2nd DSMB review. These DSMB outcome reports and

amendment(s) must be re-approved by the requiring National Competent Authority (Germany) prior to study continuation and patient enrollment in Germany if the next cohort is allowed.

If, for any reason, the sponsor suspends or prematurely terminates the investigation at an individual investigation site, the sponsor shall inform the responsible regulatory authority as appropriate and ensure that the ethics committee is notified,

If suspension or premature termination occurs, the Sponsor shall remain responsible for providing resources to fulfil the obligations from the CIP and existing agreements for following up the subjects enrolled in the clinical investigation, and the PI or authorized designee shall promptly inform the enrolled subjects at his/her investigation site, if appropriate. The method and the timing of this communication will depend on the circumstances and the perceived risks.

Appendix 1a- Acute-on-Chronic Liver Failure Grading Scheme per CLIF-OF scoring system.

Grade	Subgroups	ACLF grade equivalent (for DIALIVE study)
No ACLF*	 Patients with no organ failure Patients with a single hepatic, coagulation, circulation or respiratory failure, no AKI and no HE serum creatinine <1.5mg/dL and no hepatic encephalopathy (HE) Patients with single cerebral failure and serum creatinine <1.5mg/dL 	
Grade 1	 Patients with renal failure (sCr > 2 mg/dL) Patients with other single failure organ failure with serum creatinine ≥1.5 and <2 mg/dl and/or HE grade 1-2 	 Patients with serum bilirubin > 20 mg/dL (364 μmol/L) AKI stage 1b (sCr > 1.5 mg/dL or 134 μmol/L)
Grade 2	Patients with 2 organ failures	
Grade 3 a	Patients with 3 organ failures	
Grade 3 b	Patisents with more than 3 organ failure	

From: Moreau, R., et al., *Acute-on-chronic liver failure is a distinct syndrome that develops in patients with acute decompensation of cirrhosis.* Gastroenterology, 2013. **144**(7): p. 1426-37, 1437 e1-9.

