Clinical Investigation Plan	CIP YAQ-002	Version: 7.0 10 October 2019

Inclusion Criteria	 Male or female subjects aged ≥18 years ≤81yr
	 Subject is able to provide informed consent to participate in the study, otherwise written
	informed consent must be obtained on behalf of the subject by next of kin or a legal
	representative in accordance with local ethical and legal requirements.
	History indicative of alcohol-related cirrhosis based on clinical, radiological and/or
	histological evidence.
	 History of an acute decompensation event (including but not limited to ascites,
	gastrointestinal bleeding, hepatic encephalopathy and/or acute bacterial infections),
	occurring within ≤6 weeks of screening.
	Subject with:
	 ACLF Grade 1, 2 or 3a defined per the CLIF-C OF scoring system OR
	o single hepatic organ failure for serum bilirubin > 20 mg/dL (342 µmol/L) at
	screening and randomization, OR
	 AKI-stage 1b (sCr > 1.5 mg/dL or 134 μmol/L).
	Where a subject has received corticosteroids as specific therapy for alcohol hepatitis and
	,
	is deemed unresponsive to steroids after 7 days of treatment (lack of response defined as
	Lille score of > 0.45 or steroids stopped before 7 days due to any complication such as
	infection). This refers to the first course of corticosteorid therapy. Further courses of
	corticosteroids during the course of illness must not be used to determine steroid
	responsiveness.

Clinical Investigation Plan CIP YAQ-002 Vers	rsion: 7.0 10 October 2019
--	----------------------------

Exclusion Criteria

- Co-infection with HIV and AIDS defining illness4
- Subjects with acute or sub-acute liver failure without underlying cirrhosis.
- Subjects with severe thrombocytopaenia, as defined by the platelet count of <40,000/mm³ (at screening/randomization) or rapid reduction in platelet count (> 50% reduction) in the previous 24 hrs prior to randomisation (day 0)
- Subjects with International Normalised Ratio (INR) > 3
- ACLF 3b patients, i.e. ACLF with more than 3 organ failures.
- Subjects with cirrhosis who develop decompensation at any time in the post-operative period following partial liver resection or major non-liver surgery.
- Subjects with uncontrolled infection. Patients may be entered into the study provided antimicrobials have been administered for at least 48 hours with an appropriate response observed prior to randomization.

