- 2. If the clinical condition of a patient meets one or more study stopping criteria.

Patients considered to be a 'screen failure' or 'excluded' will remain in study for a minimum follow up period of 28 days.

Standard definitions: definitions for DIALIVE organ failure and ACLF grading per the CLIF-C OF scoring system, Lille score, and others, are given in Appendix 1-2.

Hepatic Encephalopathy (HE): determination of HE as part of ACLF grading will be based upon clinical assessment and graded as per the West Haven criteria. However, if there is ambiguity or observer variability, an EEG may be sought by the PI for supportive evidence. This is particularly relevant for grade 1 HE which may not be consistenly reproducible using the West Haven criteria, and as such is now included as part of the covert HE spectrum along with minimal HE often requiring psychometric tests or EEG for diagnosis

Specific therapy such as corticosteroids for alcoholic hepatitis can be used if a patient is already within the study and these have not been trialed previously and as long as clinical justification and rationale is clearly documented. This applies to patients in both SOC and the DIALIVE arm. For other indications of steroid use such as potential relative adrenal insufficiency, it should precede a short synacthen test, particularly in patients who are haemodynamically stable, to establish this diagnosis.

Standard of Care (SOC) is defined as the standard medical and nursing management of patients with ACLF Grades 1 and 2 as per local practices. Medical intervention is to be guided by the treating physician taking into account the overall clinical picture, precipitating event, and the nature and severity of organ dysfunction. The interventions may include (but not limited to) the supportive management with fluid therapy, including albumin therapy where indicated, antibiotics for suspected or confirmed infections, nutrition, bowel management, thromboprohylaxis, and organ system support including the use of terlipressin as splanchnic vasopressor and for cardiovascular support where indicated, oxygen and non-invasive respiratory support, laxatives and non-absorbable antibiotics for hepatic encephalopathy, and dialytic therapy for renal failure. SOC may also include urgent liver transplantation as per local practices.

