5.1.3 Secondary End Points

To evaluate the performance of the DIALIVE in patients with ACLF. This is measured by;

Change in Plasma endotoxin level (endotoxin activity and concentration) between;

D1, D3, D5 and D10 across SOC arm $\,$

D1, D3, D5 and D10 across DIALIVE arm

_

¹⁰ In case a patient's treatment is discontinued, the follow up period will remain 28 days from the moment of randomization.

Clinical Investigation Plan	CIP YAQ-002	Version: 7.0 10 October 2019
-----------------------------	-------------	------------------------------

Start and end of a treatment session (on D1, D2 and D3) with DIALIVE D1,D3, D5 and D10 between SOC and DIALIVE arms for patients presenting with the same grades of ACLF (i.e. Grade 1 ALCF compared with Grade 1 ACLF)

Target-Value (TV): 40% reduction; Acceptable-Value (AV): 20% reduction at end of treatment cycle.

• Change in Albumin function (Human non-mercapt albumin -2 (HNA-2) / Human marcapt albumin (HMA) ratio:

D1, D3, D5 and D10 across SOC arm
D1,D3, D5 and D10 across DIALIVE arm
Start and end of a treatment session (on D1, D2, D3) with DIALIVE
D1,D3, D5 and D10 between SOC and DIALIVE arms for patients presenting with the same grades of ACLF (i.e. Grade 1 ALCF compared with Grade 1 ACLF)

TV: 40% reduction; AV: 20% reduction at end of treatment cycle.

- Mortality: 28-days and 90 days
- Change in ACLF Grade
- Change in CLIF-ACLF score
- Improvement in individual organ function: Brain (HE), Kidney (creatinine), CVS (mean arterial pressure), Pulmonary (P/F ratio, or S/F if patient is not intubated), Liver (serum bilirubin) and coagulation (INR and platelets).
- Status at ICU and Hospital Discharge (including discharge to a hospice for palliative care).
- Lengths of stay in ICU and Hospital at D28 and D90
- ICU and Hospital re-admissions with another episode of ACLF up to 3 months after randomisation.

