5.3. Subjects

5.3.1. Inclusion criteria

- Male or female subjects aged ≥18 years ≤81yr
- Subject is able to provide informed consent to participate in the study, otherwise written informed consent must be
 obtained on behalf of the subject by next of kin or a legal representative in accordance with local ethical and legal
 requirements.
- History indicative of alcohol-related cirrhosis based on clinical, radiological and/or histological evidence.
- History of an acute decompensation event (including but not limited to ascites, gastrointestinal bleeding, hepatic encephalopathy and/or acute bacterial infections), occurring within ≤6 weeks of screening.
- Subject with :
 - o ACLF Grade 1, 2 or 3a defined per the CLIF-C OF score system OR
 - o single hepatic organ failure for serum bilirubin > 20 mg/dL (342 µmol/L) at screening and randomization, OR
 - \circ AKI-stage 1b (sCr > 1.5 mg/dL or 134 μ mol/L)¹².
- Where a subject has received corticosteroids for alcohol hepatitis and is deemed unresponsive to steroids after 7 days of treatment (lack of response defined as Lille score¹³ of > 0.45 or steroids stopped before 7 days due to any complication such as infection). This refers to the first course of corticosteorid therapy. Further courses of corticosteroids during the course of illness must not be used to determine steroid responsiveness.

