5.3.4. Point of enrolment

Patients will be recruited through in-patient wards across multiple European centres. Approximately one (1) patient every four (4) months per centre will be recruited with an estimated three (3) patients per centre in total, although competitive recruitment will be utilised. This recruitment strategy is based upon the data accumulated during the performance of the CANONIC study [5].

Following consent and confirmation of eligibility, patients will be randomised electronically via the eCRF . The site will be issued with the subject ID number and informed of their treatment arm. Patients will be deemed enrolled at the point of randomization (Day 0).

5.3.5. Total expected duration of the clinical investigation.

The total duration of the study will be approximately 39 months.

5.3.6. Expected duration of each subject's participation.

After signing the Informed Consent, the patient can be screened for compliance with the in/exclusion criteria for up to 3 days. Patients from cohort 1, 2 and 3 are followed for 28 days, those from cohort 4 and 5 for 90 days.

Patients will be randomized on study day 0 followed by a maximum treatment window period of 10 days (DIALIVE arm). All patients will be intensively followed during the initial 28 days post-randomization and complete the study after completion of study day 28 (cohort 1, 2 and 3) or day 90 (cohort 4 and 5)...

5.3.7. Number of subjects included in the clinical investigation.

30 evaluable subjects will be randomised to receive either standard of care (SOC) or treatment with DIALIVE (1:1 randomisation).

As this is a first-in-man trial, and no hypothesis is to be tested, the sample size is arbitrarily set to obtain adequate information in a small patient population. This reduces the total number of patients exposed to potential study related risks while allowing the investigators to learn maximally from this potential treatment for ACLF-patients for which no alternative

Clinical Investigation Plan	CIP YAQ-002	Version: 7.0 10 October 2019
-----------------------------	-------------	------------------------------

treatment exists and the Data Safety Monitoring Board to make appropriate decisions on study (dis)continuation by comparing occurrence of adverse events between control and treatment arms in each of the 5 cohorts of patients.

5.3.8. Estimated time needed to select this number (i.e. enrolment/recruitment period).

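### Appendix 1a converts bilirubin 20 mg/dL to 364 µmol/L where the rest of the protocol uses 342, so the ACLF grade label is contradictory for a narrow group at sites working in µmol/L

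*Protocol*

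**What the plan says.** Section 5.3.1 admits patients with "single hepatic organ failure for serum bilirubin > 20 mg/dL (342" µmol/L, at screening and at randomisation. The synopsis inclusion criteria repeat this. The synopsis target population lists the same route, with "serum bilirubin > 20 mg/dL (342" µmol/L, and footnote 2 there says that bilirubin rising above this level carries high mortality, equivalent to ACLF 1.

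Appendix 1a sets out the ACLF grading scheme and has a column of grade equivalents specific to this study. In its Grade 1 row that column reads "Patients with serum bilirubin > 20 mg/dL (364", again in µmol/L. The No ACLF row of the same table includes a single hepatic failure with no AKI, creatinine below 1.5 mg/dL and no hepatic encephalopathy.

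Section 2.2 sends the reader to the appendices for grading: "definitions for DIALIVE organ failure and ACLF grading per the CLIF-C OF scoring system, Lille score, and others, are given in Appendix 1-2". Grade is then used in the secondary endpoints of Section 5.1.3. Change in ACLF grade is one of them, and the between-arm comparisons of endotoxin and albumin function are made "for patients presenting with the same grades of ACLF".

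**The concern.** A single mg/dL value cannot have two µmol/L equivalents. The 20 mg/dL cut-off is constant throughout, but the figure that a µmol/L laboratory would use is 342 in the synopsis and Section 5.3.1 and 364 in the grading table.

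The higher figure is in a place that sites are told to consult: the column that adapts the published grading scheme to this trial. A patient between the two figures can enter through the bilirubin route and then receive different grade labels depending on which page is read. That label may decide whether the patient counts in the Grade 1 comparison of endotoxin and albumin function, and what baseline the change in grade is measured from. Grade is also reassessed at visits to Day 28. A patient whose bilirubin falls from above 364 into the band could therefore appear to improve by a grade on one reading and not on the other.

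**Working it through.** **Inputs**

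| Place | mg/dL | µmol/L |
|---|---|---|
| Synopsis, target population | > 20 | 342 |
| Synopsis, footnote 2 | > 20 | 342 |
| Synopsis, inclusion criteria | > 20 | 342 |
| Section 5.3.1 | > 20 | 342 |
| Appendix 1a, Grade 1 equivalent | > 20 | 364 |

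**Conversion.** µmol/L = mg/dL × factor. The protocol prints no factor, so it has to be read off each pair.

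- Synopsis and Section 5.3.1: 342 / 20 = 17.1
- Appendix 1a: 364 / 20 = 18.2

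As a cross-check from outside the documents, stated as an assumption, a bilirubin molar mass of about 584.66 g/mol gives 10,000 / 584.66 = 17.10. Then 20 × 17.10 = 342, which reproduces the figure in the synopsis and Section 5.3.1. It does not reproduce 364.

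**Sensitivity to the factor**

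| Factor | 20 mg/dL in µmol/L | 364 µmol/L in mg/dL |
|---|---|---|
| 17.0 | 340 | 21.4 |
| 17.1 | 342 | 21.3 |
| 17.2 | 344 | 21.2 |

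No factor in this range brings 20 mg/dL near 364.

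**Width of the band.** 364 − 342 = 22 µmol/L, and 22 / 342 = 6.4% of the threshold.

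**Example inside the band.** Take 350 µmol/L, which is 350 / 17.1 = 20.5 mg/dL, in a patient with isolated hepatic failure, creatinine below 1.5 mg/dL, no AKI and no encephalopathy.

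- Section 5.3.1: 350 > 342, so the bilirubin criterion is met.
- Footnote 2: above 342, so equivalent to ACLF 1.
- Appendix 1a read in mg/dL: 20.5 > 20, so Grade 1 equivalent.
- Appendix 1a read in µmol/L: 350 is not above 364, so not Grade 1 equivalent. The patient falls in the No ACLF row.

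**Who is outside the problem.** Under the ordinary Grade 1 rule in Appendix 1a, a single organ failure with creatinine from 1.5 to below 2 mg/dL, or with grade 1–2 encephalopathy, is already Grade 1 whatever the bilirubin. The CLIF-C OF liver sub-score in Appendix 1b is given in mg/dL only and reaches its top category above 12 mg/dL, so every value in the band scores 3 on either reading. The CLIF-C ACLF score, built from that organ-failure score, age and white cell count, is therefore unaffected too.

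**Weight of one patient.** With 30 evaluable patients randomised 1:1 there are 15 per arm, so one relabelled patient would be 1 / 15 = 6.7% of an arm and a larger share of a single-grade subset. This shows scale only; it does not estimate how many patients are affected.

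**The case against.** A reader might infer that the protocol has two conflicting entry thresholds, so that eligibility depends on the page a site opens. The documents do not support that. Every statement of the entry criterion gives 342. Bilirubin is a stand-alone route that does not depend on a grade, and the criterion in Section 5.3.1 carries no reference to Appendix 1a. A patient at 350 µmol/L is eligible under the criteria as written. Eligibility would differ only if a site applied the grading table in their place.

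It can also be said that the governing number, 20 mg/dL, never changes, including in Appendix 1a. The 364 is a bracketed conversion, and only a reader who takes the µmol/L figure directly from that table is misled. That stands, and it confines the problem to sites working in µmol/L. It does not remove the problem, because the protocol prints µmol/L beside mg/dL for such readers.

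A further objection is that the analysis may not use the study-specific equivalent at all. The protocol does not say whether this label or the unmodified grade enters the change-in-grade endpoint and the same-grade comparisons. That is fair, so the effect on those endpoints is possible and not established.

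Finally, the 6.4% is the width of the band relative to the threshold. It should not be read as a share of patients, since the protocol gives no bilirubin distribution.

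**Conclusion.** The inconsistency is real and stands in the current text. The 364 in Appendix 1a is not the µmol/L equivalent of 20 mg/dL. It corresponds to about 21.3 mg/dL at the factor implied by the protocol's other four statements.

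The consequence is a contradictory grade label, Grade 1 equivalent or No ACLF, for isolated hepatic failure with creatinine below 1.5 mg/dL, no encephalopathy and bilirubin above 342 and up to 364 µmol/L, at sites that grade in µmol/L. If the study-specific equivalent is the grade analysed, the label can affect the change in ACLF grade and the same-grade endotoxin and albumin comparisons. How many of the 30 patients fall in the band cannot be told from the protocol, and it may be none.

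The primary endpoints, SAE incidence and discontinuation for a SADE, do not use grade. No power or sample size figure depends on this point either, since Section 5.3.7 states that "no hypothesis is to be tested, the sample size is arbitrarily set". Severity is minor.

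**What to change.** Reconcile the µmol/L figure in Appendix 1a with the conversion of the unchanged 20 mg/dL cut-off used in the synopsis and Section 5.3.1 (20 × 17.1 = 342). This corrects a unit conversion and leaves the clinical criterion as it is.

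Then confirm that any derivation or edit check for ACLF grade in the eCRF uses the same figure. The protocol does not show which value is coded, so this is a precaution. If 364 was used, regrade any patient with bilirubin above 342 and up to 364 µmol/L before the grade-based summaries are produced.

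The cost is one number in one table and a short check of the database.
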